2.1.5.1 Adverse events variables

Adverse event observation period

- Pre-treatment AEs are AEs that developed or worsened or became serious in the pre-treatment phase
- Treatment-emergent adverse events are AEs that developed or worsened or became serious during the on-treatment period
- Post-treatment adverse events are adverse events that developed or worsened or became serious during the post-treatment period

All adverse events (including serious adverse events) will be coded to a lower-level term (LLT), preferred term (PT), high-level term (HLT), high-level group term (HLGT), and associated primary system organ class (SOC) using the version of MedDRA in effect at Sanofi at the time of database lock.

The occurrence of all AEs (including SAEs and AESIs) will be recorded from the time of signed informed consent until the end of the study.

Any SAE brought to the attention of the Investigator at any time after the end of the study for the patient and considered by him/her to be caused by the IMP with a reasonable possibility, should be reported to the monitoring team.

Adverse event of special interest

All AEs captured on the general AE form, and any specific AE forms (like the “ALT increase”, “overdose” and “pregnancy forms”) will be searched. The list of Adverse events of special interest (AESIs) will be flagged in the database using search criteria, like standardized MedDRA query (SMQ), as shown in Table 2 below.

Table 2 - AESI and search criteria

AESI	Search criteria
ECG prolongation: QTcF \geq 500 ms or QTcF prolongation > 60 ms from baseline	SMQ: Torsade de pointes/QT prolongation
Hepatic disorders: Increase in alanine transaminase (ALT)	SMQ : Drug-related hepatic disorders – comprehensive search
Pregnancy	e-CRF checkbox: Pregnancy
Overdose	e-CRF checkboxes: Symptomatic overdose, Overdose of Ferroquine (FQ), Overdose of Artefenomel (OZ439) and Overdose of NIMP

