9.2 ADVERSE EVENTS

Adverse event of special interest

An AESI) is an AE (serious or nonserious) of scientific and medical concern specific to the Sponsor's product or program, for which ongoing monitoring and immediate notification by the Investigator to the Sponsor is required. Such events may require further investigation in order to characterize and understand them. Adverse events of special interest may be added, modified or removed during a study by protocol amendment.

- **Pregnancy** of a female subject entered in a study as well as pregnancy occurring in a female partner of a male subject entered in a study with IMP/NIMP;
 - Pregnancy occurring in a female patient entered in the clinical trial or in a female partner of a male patient entered in the clinical trial. It will be qualified as an SAE only if it fulfills one of the seriousness criteria (see Appendix 4).
 - Follow-up of the pregnancy in a female participant or in a female partner of a male participant is mandatory until the outcome has been determined (see Appendix 5)
- **Symptomatic overdose** (serious or nonserious) with IMP/noninvestigational medicinal product (NIMP)
 - An overdose (accidental or intentional) with the IMP/NIMP is an event suspected by the Investigator or spontaneously notified by the patient (not based on systematic pills count) and defined as at least twice the intended dose.

Of note, asymptomatic overdose has to be reported as a standard AE.

• Increase in alanine transaminase (ALT)): ALT ≥3 ULN (if baseline ALT <ULN) or, ALT ≥2 times the baseline value (if baseline ALT ≥ULN) will be reported as AESI.

Cases of ALT >3 ULN will be monitored according to the procedures indicated in Appendix 7.

Patients with abnormal ALT values at Day 28 will be followed up until ALT returns to normal values. A PK sample will be made at time of event for OZ439 and FQ (& SSR97213) concentration measurement.

An ALT increase ≥ 3 ULN is reportable as an SAE in any of the following situation:

- Possible Hy's law: ALT or AST >3x ULN and bilirubin >2x ULN (>35% direct bilirubin) in the absence of a serum alkaline phosphatase level >2x ULN. [If fractionation is unavailable, record presence of detectable urinary bilirubin on dipstick indicating direct bilirubin elevations and suggesting liver injury]) or
- when ALT $>10 \times ULN$,
- when associated with jaundice or,
- when associated with coagulation disorder (prothrombin time <50%) or,
- in presence of signs of hepatic encephalopathy.

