- Other project specific AESI:
 - QTcF ≥500 ms or QTcF prolongation > 60 ms from baseline

In the event of QTcF interval ≥500 ms (automatic measurement) or a QTcF prolongation >60 ms (automatic measurement) from baseline, the patient should be placed under supervision in a specialized setting.

Subsequent ECG monitoring of the patient should then be performed on a regular and clinically responsible basis until the QTc interval returns to their baseline QTcF value.

In case of QTcF ≥500 ms (automatic measurement) or QTcF prolongation >60 ms from baseline, patient will have blood drawn for measurement of OZ439 and FQ (& SSR97213) concentration.

The Investigator will report an AESI only if QTcF ≥500 ms or QTcF prolongation >60 ms from baseline is confirmed by central reading.

The definitions of an AE or SAE can be found in Appendix 4.

AE will be reported by the participant (or, when appropriate, by a caregiver, surrogate, or the participant's legally authorized representative).

The investigator and any designees are responsible for detecting, documenting, and recording events that meet the definition of an AE or SAE and remain responsible for following up AEs that are serious, considered related to the study treatment or study procedures, or that caused the participant to discontinue the study (see Section 8).

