10.3.2.5 Drug-induced liver injury and QT prolongation

To prevent missing any event related to the AESI defined for the study (see Section 9.2), the selection of preferred terms will be based on standardized MedDRA queries (SMQs):

- Hepatic disorder (code 20000005, level 1, active) for potential DILI events
- Torsade de pointes/QT prolongation (code 20000001, level 1, active) for potential cardiac events

Time to liver-related treatment discontinuation and time to liver death may also be provided based on hepatic disorder SMO.

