At least grade 2	>220 ms and increase from baseline \geq 25%	
At least grade 3	>240 ms and increase from baseline \geq 25%	
QRS		
High, all grades	>110 ms	Birth/0 to 27 days old : \geq 85 ms 28 days/1 month to 23 months old: \geq 85 ms 24 months/2 years to <6 years old: \geq 95 ms 6 to <12 years old : \geq 100 ms 12 to 16/18 years old : \geq 110 ms
At least grade 1 (adults)	>110 ms	
At least grade 2 (adults)	>120 ms	
High and increase from baseline (adults)		
At least grade 1	>110 ms and increase from baseline \geq 25%	
At least grade 2	>120 ms and increase from baseline \geq 25%	
QTc Fridericia		
Increase from baseline, Grade 1	Increase from baseline]30-60] ms	All age classes: Increase from baseline (30-60] ms

ECG Parameter	Adults	Children
PCSA criteria n/N1 (%)		
Increase from baseline, Grade 2	Increase from baseline >60 ms	All age classes: Increase from baseline >60 ms

References:

- for adults: Criteria for Potentially Significant Abnormalities – for Phase 2/3 studies (oncology excepted) - Version 3.0 - 21-MAY-2014
- for children: Criteria for Potentially Clinically Significant Abnormalities for Studies in Children - Version 3.0 - 21-MAY-2014

Vital signs parameter	Adults	Children
PCSA criteria n/N1 (%)		
Systolic blood pressure supine		
Low and decrease from baseline	≤ 95 mmHg and decrease from baseline ≥ 20 mmHg	Birth/0 to 27 days old : ≤ 60 mmHg and decrease from baseline ≥ 20 mmHg 28 days/1 month to 23 months old: ≤ 70 mmHg and decrease from baseline ≥ 20 mmHg 24 months/2 years to <6 years old: ≤ 70 mmHg and decrease from baseline ≥ 20 mmHg 6 to <12 years old : ≤ 80 mmHg and decrease from baseline ≥ 20 mmHg 12 to 16/18 years old : ≤ 90 mmHg and decrease from baseline ≥ 20 mmHg
High and increase from baseline	≥ 160 mmHg and increase from baseline ≥ 20 mmHg	Birth/0 to 27 days old : ≥ 85 mmHg and increase from baseline ≥ 20 mmHg 28 days/1 month to 23 months old: ≥ 98 mmHg and increase from baseline ≥ 20 mmHg 24 months/2 years to <6 years old: ≥ 101 mmHg and increase from baseline ≥ 20 mmHg 6 to <12 years old : ≥ 108 mmHg and increase from baseline ≥ 20 mmHg 12 to 16/18 years old : ≥ 119 mmHg and increase from baseline ≥ 20 mmHg
Diastolic blood pressure supine		
Low and decrease from baseline	≤ 45 mmHg and decrease from baseline ≥ 10 mmHg	Birth/0 to <6 years old : ≤ 34 mmHg and decrease from baseline ≥ 10 mmHg 6 to <12 years old : ≤ 48 mmHg and decrease from baseline ≥ 10 mmHg 12 to 16/18 years old : ≤ 54 mmHg and decrease from baseline ≥ 10 mmHg

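### The SAP uses an SMQ hit as the flag for hepatic and QT AESIs without applying the protocol's ALT and QTcF thresholds, so the by-arm AESI table can count sub-threshold events

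*SAP*

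**What the plan says.** **Protocol.** Section 9.2 sets the hepatic AESI by value: "ALT ≥3 ULN (if baseline ALT <ULN) or, ALT ≥2 times the baseline value (if baseline ALT ≥ULN) will be reported as AESI". For QT it says: "The Investigator will report an AESI only if QTcF ≥500 ms or QTcF prolongation >60 ms from baseline is confirmed by central reading". Table 9 (Section 10.3.2) plans a participant count and percentage for each AESI by arm, and lists liver-related adverse events as a separate item. Section 10.3.2.5 then brings in SMQs, with this stated aim: "To prevent missing any event related to the AESI defined for the study". It refers back to Section 9.2 for the definition. Its hepatic query is "Hepatic disorder (code 20000005, level 1, active) for potential DILI events".

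**SAP.** Section 2.1.5.1 searches the general adverse event form and the specific forms, naming one for ALT increase. AESIs "will be flagged in the database using search criteria, like standardized MedDRA query (SMQ), as shown in Table 2 below". In Table 2 the QT row carries the two QTcF limits in its label and the torsade/QT SMQ as its search. The hepatic row names an ALT increase with no value attached, and its search is the SMQ Drug-related hepatic disorders – comprehensive search. Section 2.4.5.1 tabulates treatment-emergent AESIs by preferred term within category, and adds separate tables for hepatic disorders and for torsade/QT prolongation. Section 1.6, which lists changes from the protocol's statistical section, does not mention the hepatic SMQ.

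**The concern.** A coded preferred term carries no magnitude. If membership of an SMQ is what sets the flag, a liver or QT term recorded for a value below the protocol limit counts as an AESI in the same way as a true crossing. Nothing in the SAP removes it afterwards, and nothing in the SAP derives the flag from ALT or QTcF values.

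Protocol 3.3 names liver enzyme elevation and QTcF prolongation as the identified risks of both components. The by-arm AESI count is where a reader would look for a relation to OZ439 dose. If that count does not follow the protocol definition, the CSR will show an AESI rate that cannot be interpreted against the protocol's thresholds.

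**Working it through.** The plan states no figure to reproduce. The check compares definitions and does some threshold arithmetic.

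**1. Role of the SMQ in each document.** In the protocol, Section 9.2 defines the AESI and Section 10.3.2.5 adds the SMQ as a safety net around that definition. In the SAP, the SMQ is the flag. The QTcF limits survive only as a row label, and the ALT limits do not appear in Table 2.

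**2. Which events enter the SAP's AESI table.**
- *Over-inclusion* needs only one sub-threshold liver or QT term that falls within the SMQ.
- *Omission* needs a crossing that was never reported. Protocol 9.2 requires ALT crossings and centrally confirmed QTcF crossings to be reported as AESIs, and the SAP searches the forms on which they would be entered.

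**3. Whether the ALT PCSA table gives the missing count.** Inputs: exclusion E16 bars ALT above 2 ULN; the AESI rule is in Protocol 9.2; the adult ALT PCSA (SAP Appendix B) starts at >3 ULN. Let *b* be baseline ALT in ULN, with 1 ≤ *b* ≤ 2.

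AESI cut-off = 2*b*, so it runs from 2 × 1 = 2 ULN to 2 × 2 = 4 ULN. It equals the PCSA limit only at *b* = 3/2 = 1.5.

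| Baseline (ULN) | On-study ALT (ULN) | AESI cut-off | AESI? | Adult PCSA (>3)? |
|---|---|---|---|---|
| 1.2 | 2.5 | 2.4 | yes | no |
| 1.8 | 3.2 | 3.6 | no | yes |

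The two rules disagree in both directions. For baseline below ULN they agree in adults except at exactly 3 ULN (≥3 against >3).

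**4. Whether the QTcF PCSA table gives it.** Appendix B has two QTcF classes, a rise above 30 and up to 60 ms, and "Increase from baseline >60 ms". There is no absolute limit. The >60 ms part of the AESI is therefore counted by arm, and the ≥500 ms part is not. Exclusion E18 bars baseline QTcF above 450 ms. A value ≥500 ms with a rise ≤60 ms needs baseline ≥ 500 − 60 = 440 ms. The uncovered region is therefore baseline 440–450 ms with QTcF 500–510 ms (450 + 60 = 510). Example: 446 to 502 ms is a rise of 56 ms, an AESI that falls in the 30–60 ms class. Its absolute value would be seen in individual listings (SAP 2.4.5.5 lists values above 480 ms), but in no by-arm count unless it was reported as an adverse event.

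**5. Hepatic query.** The protocol gives Hepatic disorder, code 20000005. The SAP gives Drug-related hepatic disorders – comprehensive search. The names differ and SAP 1.6 is silent.

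**6. Scale.** With about 35 participants randomized per arm, one misclassified participant changes an arm's AESI percentage by 1/35 = 2.9 percentage points.

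**The case against.** The strongest defence is that SMQ selection is the protocol's own method. Section 10.3.2.5 prescribes it for these AESIs, so a reader who infers that the SAP brought in SMQs against the protocol would be wrong. That part of the defence stands. It does not justify the flag: the protocol's stated aim is to avoid missing events already defined in Section 9.2, and a net to prevent omissions does not turn everything it catches into an AESI.

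A second defence is that Table 2's left column defines the AESI and the right column is only a search tool. That is arguable for QT, where the limits are printed. It is weak for ALT, where they are not. In neither row is there a step that compares a hit with a limit.

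Three stronger readings are tempting and the documents do not support them:
- *That measured crossings are systematically missed.* Reporting is mandatory, AESIs go to the sponsor within 24 hours (Protocol 9.2.1), and the ALT-increase form is searched. Omission requires non-reporting.
- *That an ALT AESI between 2 and 3 ULN appears nowhere.* If reported as required, it is in the adverse event tables. Measured ALT also appears in by-visit and worst-value summaries by arm and on the e-DISH plot (SAP 2.4.5.3).
- *That the QTcF gap is wide.* E18 confines it to rises of 50–60 ms.

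It is also fair that safety analyses are descriptive, that a listing can be counted by hand at this sample size, and that the documents do not show how far the two hepatic SMQs differ in content.

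**Conclusion.** The point holds in limited form. As written, the SAP's by-arm AESI table can count hepatic and QT terms that do not meet Protocol 9.2, and no other planned by-arm table gives the protocol-defined count. If the separate hepatic and QT tables in SAP 2.4.5.1 use the same SMQs, which the SAP does not state, the AESI table will largely repeat them. The unlisted change of hepatic SMQ is a plain discrepancy between the documents.

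The number of affected participants cannot be derived from the documents. The QTcF region in step 4 of the working assumes that the analysis baseline respects E18. Protocol 9.4.3 bases E18 on the automatic screening value, while SAP 2.1.5.5 takes the Day 0 triplicate mean as baseline, so a baseline somewhat above 450 ms is possible and would widen the region. No hypothesis test is affected. What is affected is the main display of the two identified risks.

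**What to change.** In SAP 2.1.5.1 Table 2:
- Derive the ALT AESI flag from laboratory values and baseline, using both limbs of the Protocol 9.2 rule.
- Derive the QTcF AESI flag from the central readings, with ≥500 ms or a rise >60 ms. State that the triplicate mean is used, as in SAP 2.1.5.5, because Protocol 9.2 asks for central confirmation without specifying the mean.
- Reconcile both flags with the AESI forms and list any disagreement.

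Keep the SMQ output as separate supportive tables. Either return to the protocol's hepatic SMQ or list the change in SAP 1.6. Add a by-arm row for QTcF ≥500 ms to the ECG PCSA table.

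The cost is SAP wording, two derived flags and one table row, all from data already collected. No AESI definition, reporting duty or clinical rule changes.

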2.1.5.2 Deaths

The deaths observation period is per the observation periods defined below.

- Death on-study: deaths occurring during the on-study observation period
- Death on-treatment: deaths occurring during the on treatment period
- Death post-study: deaths occurring after the end of the study

2.1.5.3 Laboratory safety variables

Clinical laboratory data consists of blood analysis, including hematology, clinical chemistry, and urinalysis. Local clinical laboratory values after conversion will be analyzed into standard international units and international units will be used in all listings and tables.

Blood samples for clinical laboratories will be done locally at Visit 1 (Screening/pre-dose), Visit 4 (Day 2 hour 48), Visit 5 (Day 3 hour 72) only if patient still hospitalized, Visit 6 (Day 3 hour 96) only if patient still hospitalized, Visit 9 (Day 7 hour 168), Visit 11 (Day 14), Visit 12 (Day 21) and Visit 13 (Day 28) unless otherwise specified. The laboratory parameters will be classified as follows:

- Hematology
 - **Red blood cells and platelets and coagulation:** hemoglobin, hematocrit, reticulocytes (not needed at screening), haptoglobin (not needed at screening), red blood cell count, platelet count.
 - **White blood cells:** white blood cell count, neutrophils, lymphocytes, monocytes, basophils, eosinophils
- Clinical chemistry
 - **Metabolism:** glucose, albumin, creatine phosphokinase
 - **Electrolytes:** sodium, potassium, calcium, magnesium
 - **Renal function:** creatinine, creatinine clearance, urea
 - **Liver function:** alanine aminotransferase (ALT), aspartate aminotransferase (AST), alkaline phosphatase (ALP), lactate dehydrogenase, total bilirubin (TBIL) and direct bilirubin (BILDIR, not needed at screening)
 - **Pregnancy test (screen):** Serum or urine β -human chorionic gonadotropin (all female patients)
 - **Viral hepatitis serology (screen):** HAV IgM, HBsAg, HCV Ab, and/or HCV RNA

Urine samples will be collected as follows:

- **Urinalysis** - quantitative analyses: pH, specific gravity, proteins, glucose, blood, ketones, bilirubin, leukocyte esterase by dipstick. Microscopic examination (if blood or protein is abnormal)

Creatinine clearance is calculated locally according to formulae specified in the protocol:

- Cockroft and Gault formula for patients more than 18 y.o.
- GFR Bedside Schwartz formula for patients between 14 y.o and <18 y.o.

Technical formulas are described in Section 2.5.1.

2.1.5.4 Vital signs variables

Vital signs include heart rate, systolic and diastolic blood pressure (SBP and DBP), temperature and weight. At each visit where blood pressure is scheduled i.e. Visit 1 (Screening/Pre-dose), Visit 2 [hour 6 and 12), Visit 3 (hour 24), Visit 4 (hour 48), Visit 5 (hour 72) only if patient still hospitalized, Visit 6 (hour 96) only if patient still hospitalized, Visit 8 (hour 144), Visit 9 (hour 168), Visit 10 (Day 10), Visit 11 (Day 14), Visit 12 (Day 21) and Visit 13 (Day 28), three assessments, at least 1 minute apart, will be performed and recorded on the e-CRF as the average of the 3 blood pressure readings according to procedures described in the protocol according to supine position.

2.1.5.5 ECG variables

A 12-lead ECG recording on Visit 2 (Day 0 hour 0, 2, 4, 6, 8, 12), Visit 3 (Day 1 hour 24), Visit 4 (Day 2 hour 48), Visit 5 (Day 3 hour 72) only if patient still hospitalized, Visit 6 (Day 4 hour 96) only if patient still hospitalized and Visit 9 (Day 7 hour 96), using a 12-lead ECG to extract triplicate measurements at each theoretical time point (each replicate record will be centrally read by a Core Lab Banook group (semi-automatic reading). The parameters that will be received from the ECG reading center are: RR, QT, QTcF, QTcB, PR and QRS (msec) and heart rate (bpm), but also ST deviation, T-wave morphology, U wave presence or absence.

All ECGs (triplicate) will be manually read by independent experts (except Visit 1 (Screen) for which automatic reading will be done).

For all quantitative ECG parameters, the mean of triplicate ECGs at each time point will be used for all analyses including PCSA analyses. As far as at least one record is available from a triplicate, it will be used in the mean calculations for analyses. No time restriction is applied for calculation of mean values from triplicate ECGs performed at the same visit.

For each set of triplicate ECGs, the associated date and time of the assessment is taken as the date and time of the first record of the triplicate.

The value to be used as baseline will be defined as the average of the triplicate assessments done on Day 0 T0 or the last available time point prior to first dosing for each treatment group.

2.1.6 Pharmacokinetic variables

Concentrations of OZ439 in plasma and of FQ and its metabolite SSR97213 in blood will be evaluated at specific time points.

The PK parameters will be estimated through Bayesian analysis using previously developed population PK models. Please see Appendix C for references.

The Bayesian PK analyses for OZ439 and for FQ and SSR97213 will be described in a separate analysis plan. The detailed pharmacokinetic analyses will be reported separately from the main CSR. A summary of the methods and results will be reported in the main CSR.

The list of pharmacokinetics parameters for OZ439 in plasma, and for FQ and SSR97213 in blood are the following:

- C_{max} , t_{max} , C_{168h} , and AUC
- $AUC_{0-day28}$ for FQ and SSR97213 only

2.1.7 Further therapy after discontinuation of investigational medicinal product administration during the study

A period of time Day 0 - Day 28, in line with efficacy time points, will be considered for anti-malarial medications other than investigational medicinal product.

Day 0 - Day 28 is defined as the period of time starting the first IMP intake day and ending with the Day 28 time window defined in [Section 2.5.4.1](#).

2.2 DISPOSITION OF PATIENTS

This section describes patient disposition for both patient study status and the patient analysis populations.

Screened patients are defined as any patients who met the inclusion criteria and signed the informed consent form (ICF).

Randomized patients consist of all patients with a signed informed consent form who have had a treatment kit number allocated and recorded in the IRT database (IVRS_H hybrid SDTM dataset), regardless of whether the treatment kit was used. Patients treated without being randomized by Interactive Voice Response System/Interactive Web Response System (IVRS/IWRS) will not be considered as randomized and will not be included in any population.

In the unlikely event of any patient being randomized more than once, only the data associated with the first randomization will be used in any analysis population. The safety experience associated with any later randomization will be assessed separately.

For patient study status, the total number of patients in each of the following categories will be presented in the clinical study report using a flowchart diagram or summary table by treatment group:

- Randomized and not treated patients

- Randomized and treated patients
- Patients who did not complete the study treatment period as per protocol
- Patients who discontinued study treatment by main reason for permanent treatment discontinuation; (patients who will receive FQ but partially OZ439 or not OZ439 at all regarding FQ+OZ439 groups)
- Reason for treatment discontinuation
- Status at last study contact (Alive/dead)

For all categories of patients (except for the screened) percentages will be calculated using the number of randomized patients as the denominator.

A detailed description of patient recruitment including number of subjects screened, randomized, treated, treated and discontinued will be summarized in a summary table by country/site.

A patient is considered lost to follow-up at the end of the study if he/she repeatedly fails to return for scheduled visits and is unable to be contacted by the study site.

All critical or major deviations potentially impacting efficacy analyses, randomization, and drug-dispensing irregularities, and other major or critical deviations will be summarized in tables giving numbers and percentages of deviations by treatment group.

Additionally, the analysis populations for safety, efficacy, and pharmacokinetics, pharmacokinetics/pharmacodynamics will be summarized in a table by number of patients in the randomized population.

- Safety population
- Modified intent-to-treat population (mITT)
- Per-protocol population (PP)
- Pharmacokinetics population
- Pharmacokinetics/pharmacodynamics efficacy population (Primary efficacy population)
- Pharmacokinetics/pharmacodynamics safety population

